
### 1.6 Methods

#### 5.6.1 Stool Measurements

Sample collection and processing: Participants receive a stool collection kit, including a plastic collection/storage container, insulated bag, and cooling elements. Patients will collect one stool sample within 24 h before the study appointment (donors) or prior to the 2-day preparation for the colonoscopy (patients). Stools will be placed in the participant's home refrigerator (+4°C) immediately after defecation. Within 24 h (up to 48 h acceptable) the stool will be brought to hospital in the insulated bag with cooling elements, where the stool will be transferred into sterile sample bags and homogenized a stomacher. In the autologous FMT group and in the donors, 150 g of the stool will be processed for FMT as described above. Another stool sample will be collected within 72 hours prior to colonoscopy preparation and stored in patient's freezer. The sample will be stored in our -80°C freezer and then homogenized and separated. Two tubes containing 20 mg each will be stored for stool metabolomics. Three tubes of about 0.1 g stool will be stored for IM measurement, and the rest will be aliquoted in 10-20 mL tubes and stored for potential future analysis. All samples, except for FMT filtrate, will be stored at -80°C until analysis.

Protocol FMT, Version 10 May 2020

Intestinal microbiome (IM): DNA extraction: DNA will be extracted from samples using the PowerSoil® DNA Isolation Kit aiming for 100 mg of sample for stool and the entire sample for plaque (MO BIO Laboratories, Inc., Carlsbad, CA). The extraction protocol will be modified to include a lysozyme digestion step (incubation at 37°C for 30 minutes) (139). DNA concentration and purity will be measured using a Nanodrop Spectrophotometer (Thermo Scientific, Rockford, IL). Extracted DNA will be stored at -20°C until analysis.

*Amplification and sequencing:* Samples will be processed according to our standard operating procedures and existing pipeline (https://github.com/ggloor/miseq\_bin). The workflow will be frozen as a release at the outset of the analysis so that all analyses are conducted using the same protocol and software versions. The current protocol is in brief as follows. DNA samples are amplified with barcoded primers specific for the V4 rRNA gene variable region using the Earth Microbiome Primers modified to have combinatorial inline barcodes (140). Post-polymerase chain reaction (PCR) samples are pooled in equimolar amounts, merged into a single library, and paired-end sequenced on an Illumina MiSeq using the version 3 chemistry. Samples are overlapped, chimeric sequences removed, and operational taxonomic units (OTUs) determined by the USEARCH set of integrated tools (141). These are instantiated in our existing pipeline. As a complementary approach, we will use DADA2, which generates unique sequences corresponding to strain level variation in the input samples (142). In either case, singleton sequences and OTUs that are less than 0.1% abundant in any sample will be discarded, and tables result that contain the number of reads mapping to a particular taxonomic group in each sample.

*Statistical analyses for IM* will be done using a compositional data analysis paradigm to acknowledge the distortion of the data that arises due to high throughput sequencing (143-148). This approach has the advantage of simultaneously adjusting for read depth differences between samples (144, 148). Exploratory data analysis will be done using compositional biplots (149, 150) that simultaneously display in a semi-quantitative manner the variation in the samples and in the taxonomic groups using an approach similar to that described by Gloor and colleagues (151, 152). Data will be examined and adjusted for any batch effects using an approach taken for microarray and RNA-seq analyses (153).

Differential abundance between groups will be determined using the ALDEx2 package using either the pairwise or glm methods that accounts for both the distortion in the data and the uncertainty of measurement inherent in these samples (144, 151). We will use an effect-size approach (154), rather than use p-values for significance testing, since effect sizes are known to be more reproducible and predictive in multivariate datasets (155). Since collection of whole metagenome sequence or whole meta-transcriptomes would be prohibitively expensive for the entire number of samples, we propose to use 16S rRNA gene profiles to impute metagenome function and pathway abundance tables using the PICRUSt tool (156), and further downstream analyses of function using a compositional approach as done previously (157).

The internal correlation structure of the microbial communities will be examined using the SPIEC-EASI tool that assumes a sparse and highly compositionally-correlated structure (147). Should the sparsity assumption not be met, we will use the phi-statistic developed by Lovell (148) which is useful for non-sparse compositional data.

*Functional microbiome analysis:* We will determine the full microbial DNA sequence of the subset of 6 patients at 0 and 3 months, using paired-end sequencing on the Illumina HiSeq. This will serve as internal control for the PICRUSt imputed data and allow us to uncover novel functions that are not represented in existing sequenced genomes. We aim to recover 75 million bacterial reads per sample, and assuming 25% human contamination after depleting methylated DNA, we anticipate multiplexing 2 samples per HiSeq lane. Reads will be assessed for microbiome composition using MetaPhlAn2 (158) and a library

encompassing unique genes for the dataset will be produces and processed as for a recent metatranscriptomic study of vaginal microbial community (157). Reads that are not assigned with this pipeline will be assembled using the Trinity assembly pipeline and assembled fragments will be compared to existing genes to determine if there are any novel functions (159). We have a dedicated 64 core computer with 128 GB of RAM available through SharcNet for this task. Differential abundance of functions and pathways will be examined using the ALDEx2 tool (145, 160) and LEfSe (161) for the imputed data.

Metabolomics analysis: Fecal samples will be collected and stored at -80°C until metabolomics analysis via nuclear magnetic resonance (NMR) spectrometry. Fecal extracts will be prepared by mixing 20 mg of frozen fecal material with 1 mL of saline phosphate buffer in D2O (deuterium oxide), followed by centrifugation (18,000×g, 1 min). Fecal supernatants will be removed and filtered through 0.2 µm membrane filters as described by Le Gall and colleagues (163). The samples will be transferred to a standard NMR tube for H-NMR spectral analysis on a 500 MHz Inova spectrometer. Spectral fitting for metabolites will be done using the standard Chenomx 500 MHz metabolite library. Typically 90% of visible peaks are assigned to a compound and more than 90% of the spectral area can be routinely fit using the Chenomx spectral analysis software. These methods have been perfected at the Metabolomic Innovation Centre (164). As for the full microbial DNA sequencing, this measurement will only be performed, if additional funding can be acquired.

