# **1 MATERIAL AND METHODS**

#### 1.1 Study Design

This will be a double-blind, placebo controlled randomized controlled trial. Morbidly obese men and women with IR who are eligible for bariatric surgery but did not perform such procedure will be approached. Those consenting will be randomly assigned to either allogenic FMT (prepared from stool donated by healthy lean donors with BMI <23 kg/m^2, matched for gender with the recipient) or autologous FMT (re-infusion of own collected feces; placebo). We plan to randomize 30 patients. Stool, blood, anthropometric measurements, questionnaires, quality of life, depression and anxiety will be assessed and will be collected before FMT and at 1 and 3 months post FMT. At baseline a physical examination will be performed, and will also be preformed if symptoms are present 3-months post-FMT . OM will be assessed before FMT and 3-months post FMT. Intestinal mucosa biopsies will be collected during colonoscopy for FMT administration as well as samples for safety.

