### **1.2 Outcomes**

#### Main outcome: Insulin resistance (HOMA-IR)

Secondary outcomes: weight (absolute number, BMI, % change), appetite score, quality of life, anxiety and depression scores

*Other measurements:* HbA1c, C-peptide, IM in stools (composition and metagenome), amount of selected groups of microorganisms measured by qPCR, blood lipids, gut hormones, blood pressure, physical examination, food intake (energy and % of energy from fat, carbohydrates, protein, fiber intake (g/d)), physical activity (units/day), environmental questionnaire, stool and serum metabolomics.

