Due to the control arm receiving autologous FMT, we are using frozen fecal filtrate. Patients need to prepare for FMT colonoscopy following standard instructions with clear fluids and a laxative the day before the procedure to clean the colon (*see colonoscopy preparation instructions*). The stool for FMT has to be collected before the adjustment of diet and bowel preparation in order to maintain the original IM (stool need to be collected no later than 3 to 4 days prior to colonoscopy). The use of an autologous FMT control group is essential, as the bowel preparation and colonoscopy itself can induce changes to the IM (134, 135). Lean donor stool will be processed the same way as the autologous stool. Freezing stool by adding glycerol as a cryoprotectant has been shown to yield active FMT preparations (136, 138). Costello and colleagues (133) examined the long-term stability of frozen stools for FMT and confirmed that fecal filtrate for treatment of *C. difficile* infection could safely be stored frozen in 10% glycerol for at least 6 months without loss of clinical efficacy or viability in the six bacterial groups tested. In our study, we will store fecal filtrate for a maximum of 3 months before using it for FMT.

We will follow patients for 3 months post FMT. Vrieze et al. found improvements in IR already 6 weeks after FMT, without weight loss (26). We will extend the observation period, as 6 weeks might not have been sufficient to cause significant weight loss. In addition, we want to see, whether FMT leads to sustainable improvements in IR and IM. Patients will be approached by the MTOP Team and will be offered a 3 years follow-up post-FMT (REB# 16-5404-AE, separate consent form).

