Morbidly obese patients: Patients will be approached if they have attended the information session and signed the psychosocial study consent where they agree to be contacted for future research studies. We will be targeting specifically those patients who decide not to go ahead with the bariatric surgery at this point in time (i.e. no follow-up arranged four weeks after the orientation session). Patients interested in our study calling us on their own initiative will be screened even if not previously evaluated by the Bariatric Clinic at TWH as long as they fulfil all other requirements. After a short phone screening, the patients receive a copy of the consent form, which will be discussed over the phone by the study coordinator. Then they will come to the hospital for the screening visit, where their medical history and medications are recorded and HOMA-IR will be measured to assess eligibility. Patients will be provided with forms for food records, activity log, environmental questionnaire, and a stool collection kit. If the patient lives far or specifically request it, he can have blood works done in an outside lab and kit will be mailed home. In this case medical history and medications are recorded over the phone. Once eligibility is confirmed depending on HOMA-IR measured at screening, patients will be called back for the baseline visit. The following will be assessed: bloodwork, anthropometric measurements, appetite rating, psychological MINI interview, depression, anxiety, and quality of life questionnaires. Then, an FMT appointment will be scheduled and patients will be randomized. Patients will collect stool samples adequate for a single transplant (150gr) before they start the bowel preparation for the colonoscopy. In the week before the stool sample is collected, they will complete the questionnaires provided at baseline. When they bring their stool sample to the hospital, completed forms will be collected, anthropometric measurements will be performed. Baseline measurements will be repeated at 1 and 3 months post FMT, except for quality of life, depression and anxiety scores.. After FMT patients are required to fill-in a symptoms diary to keep track of any AE possibly occurring. In addition, during the colonoscopy performed to administer FMT, mucosal samples will be taken from the rectum, the colon, and the terminal ileum to assess the mucosa-associated microbiome. Blood and colon secretions will be collected to evaluate the baseline immune status of the subject (infections existing prior to FMT) and colon secretions will be also stored for future research.

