### 5.7.2 Statistical analysis plans

A descriptive summary of all measurements will first be compiled using appropriate graphical representations, and means, standard deviations and proportions will be calculated. Baseline characteristics of the randomized groups will be compared to ensure balance on the important variables (e.g. HOMA, BMI). Trajectory plots will be created to examine visually the changes over time.

The changes in the outcome variables of (HOMA-IR, weight, scores for appetite, quality of life, anxiety, and depression) within the two FTM groups (allogenic vs. autologous) will be compared using generalized linear mixed models (GLMM), where the within and between groups changes over time will be examined simultaneously. Factors with known influence on the outcomes will be examined for possible inclusion in our multivariate models as covariates, particularly if found imbalanced between the randomized groups. For patient drop-out, we will check missingness patterns and employ appropriate methods of handling missing data (181). The relationships between changes in outcomes and IM will first be investigated using correlation analysis (Spearman and Pearson correlation coefficients, Chi-square and Fischer exact tests as appropriate), and subsequently using methods for correlated data when considering multiple measures (incl. covariates, multiple time points, etc.). For the latter, we will employ generalized linear and nonlinear mixed models, as well as the generalized estimating equations approach. Goodness-of-fit tests will be applied for model diagnostics (182). In addition, principal component analysis (183), co-inertia analysis will be considered when investigating possible strategies for dimension reduction (where large numbers of variables may be correlated).

Statistical analyses will be performed using SAS 9.4 and R 3.2 (or subsequent versions as they become available), and all tests will be two-sided with a significance level of 5%. Where necessary, p-value adjustments for multiple testing (e.g. Holm's Bonferroni Step-down, Benjamini and Hochberg False Discovery Rate) will be employed (184).

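### The ALDEx2 between-arm microbiome comparison states no time point, baseline adjustment or handling of a patient's repeat samples, so the pre-FMT stool may go unused

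*Combined protocol and SAP*

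**What the plan says.** All references are to the combined protocol and SAP.

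- **Sampling.** Section 1.1 says that stool, with other measurements, "will be assessed and will be collected before FMT and at 1 and 3 months post FMT". Section 1.5 agrees: "Baseline measurements will be repeated at 1 and 3 months post FMT". Each patient can therefore supply three stool samples.
- **Between-arm method.** The differential abundance paragraph of section 5.6.1 reads: "Differential abundance between groups will be determined using the ALDEx2 package using either the pairwise or glm methods". No model formula, visit, covariate or patient term follows, and the choice between the two methods is left open.
- **Criterion.** The same paragraph continues: "We will use an effect-size approach (154), rather than use p-values for significance testing". No effect-size threshold is given.
- **Longitudinal model.** The mixed model in section 5.7.2 covers "HOMA-IR, weight, scores for appetite, quality of life, anxiety, and depression". The IM is not in that list. The section does plan mixed models and generalized estimating equations involving the IM, but for its association with changes in the outcomes, which is a different question from whether the arms differ.
- **Status.** Section 1.2 puts "IM in stools (composition and metagenome), amount of selected groups of microorganisms measured by qPCR" under other measurements, below the main and secondary outcomes. Section 1.4.4, explaining the 3-month follow-up, says "we want to see, whether FMT leads to sustainable improvements in IR and IM".

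**The concern.** The question in section 1.4.4 is about change that lasts, and the samples needed to measure change are already planned. The one sentence that governs the between-arm comparison does not say how change enters. Two things follow.

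First, a literal reading allows a comparison of the arms at a follow-up visit that ignores each patient's own starting abundance of the same taxon. With about 15 patients per arm, that could discard much of the available precision.

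Second, the visit, the method and the model terms can all be chosen after the data are seen. Because taxa are to be judged by effect size with no stated threshold, those choices and the sampling error of each estimate would largely decide which taxa are reported.

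**Working it through.** **Inputs from the documents.** Section 5.7.1 plans 36 randomized, 18 per arm, and assumes 15 per arm finish after 20% attrition. The figure reproduces within rounding: 15 × 1.2 = 18, and in the other direction 18 × 0.8 = 14.4. Section 5.7.2 sets two-sided 5%. No power, SD or effect size is given for the microbiome comparison, so there is no stated figure to reproduce. (Section 1.1 gives 30 randomized instead of 36, which needs reconciling separately. I use 15 finishers per arm.)

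**Assumptions.** 80% power; one taxon; differences in SD units of the log-ratio abundance; within-patient correlation ρ between pre-FMT and follow-up values of 0.3 to 0.8, taken as equal in both arms. The documents do not give ρ.

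**Step 1: one follow-up sample, no baseline.** The standard error of the arm difference is √(2/15) = 0.365 SD. The two-sample t-test (28 degrees of freedom) gives a detectable difference of 1.06 SD. The normal approximation gives (1.960 + 0.842) × 0.365 = 1.02 SD.

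**Step 2: the same sample, adjusted for baseline.** The residual variance is multiplied by 1 − ρ², so the detectable difference is multiplied by √(1 − ρ²).

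| ρ | 1 − ρ² | Detectable difference, t-based | Normal approximation |
|---|---|---|---|
| no baseline | 1 | 1.06 SD | 1.02 SD |
| 0.3 | 0.91 | 1.01 SD | 0.98 SD |
| 0.5 | 0.75 | 0.92 SD | 0.89 SD |
| 0.7 | 0.51 | 0.76 SD | 0.73 SD |
| 0.8 | 0.36 | 0.64 SD | 0.61 SD |

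The gain is small at ρ = 0.3 and large from about 0.7.

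**Step 3: what this means for an effect-size ranking.** Take a taxon with no true arm difference and, for illustration only, a cut-off of 0.5 SD. Without baseline the chance of an observed difference beyond it is 2 × [1 − Φ(0.5/0.365)] = 17%. With adjustment the standard error is 0.365 × √(1 − ρ²), and the chance falls to 15%, 11%, 5.5% and 2.2% at ρ = 0.3, 0.5, 0.7 and 0.8. Setting p-values aside does not remove the cost of lost precision.

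**Step 4: if the 1- and 3-month samples were pooled as independent.** The plan does not say this will be done; the step only shows why a rule is needed. Here ρ is the correlation between the two follow-up samples, over the same assumed range. The design effect for two samples per patient is 1 + ρ. The 60 samples from 30 patients carry the information of 60/(1 + ρ), that is 46 at ρ = 0.3 and 33 at ρ = 0.8. Intervals that ignore this are 1/√(1 + ρ) of their proper width, 0.88 to 0.75, so about 12% to 25% too narrow.

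**The case against.** The strongest case against is that the plan is silent and nothing in it is wrong. A glm can carry a baseline covariate, and the plan does not define pairwise, which could mean paired within patient. Section 5.7.2 shows that the team knows how to handle repeated measures. The IM is an exploratory measurement in what section 5.7.1 calls a pilot. Most of this stands, and it rules out four stronger readings that a reader might infer.

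- **That the plan leaves out patient and baseline terms by design.** It does not exclude them; it does not mention them.
- **That repeat samples will be treated as independent, inflating the type I error.** Under such pooling, a nominal 5% test would reject 8.6% to 14.4% of the time for ρ from 0.3 to 0.8. That needs both pooling and a significance test. The plan never states the first, and section 5.6.1 sets the second aside. At most, the precision of the effect sizes would be overstated.
- **That chance baseline differences would bias the follow-up comparison.** In a randomized comparison at a single visit they are ordinary sampling error, already inside the unadjusted standard error. Leaving out the baseline costs precision only.
- **That a main aim of the trial is compromised.** The sentence in section 1.4.4 justifies the length of follow-up and does not rank objectives.

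The size of the gain is also uncertain. Section 1.4.4 notes that bowel preparation and colonoscopy can alter the IM, and allogenic FMT is meant to alter it, so ρ may be low, especially in that arm.

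The objection does not close the gap. The correlated-data methods in section 5.7.2 address the outcome–IM association, and no other section supplies the visit, the baseline term or the rule for repeat samples in the between-arm contrast.

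**Conclusion.** The point holds as under-specification of an exploratory analysis, with a clear and cheap improvement available. The between-arm abundance comparison lacks a time point, a stated use of the pre-FMT sample and a rule for repeat samples. With 15 per arm, a plain follow-up comparison is valid but detects about 1.06 SD, against 1.01 to 0.64 SD with baseline adjustment for ρ from 0.3 to 0.8. These figures rest on the assumed ρ, a common ρ and variance in the two arms, 80% power and one taxon at a time. If ρ is near 0.3 the gain is slight. HOMA-IR and the secondary outcomes are unaffected.

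**What to change.** Add a few sentences to the differential abundance paragraph of section 5.6.1, or to section 5.7.2:

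1. Name the 3-month between-arm contrast as the main microbiome comparison, and analyse 1 month separately.
2. Use one row per patient. For each taxon, regress the 3-month centred log-ratio (clr) value on arm plus the same taxon's pre-FMT clr value, averaging over the ALDEx2 Monte-Carlo instances.
3. Report the arm effect size with a confidence interval. Benjamini-Hochberg q-values are optional, since the plan deliberately relies on effect sizes.

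The cost is SAP wording and a short script around the existing pipeline; no new samples are needed. The downside is that patients lacking a pre-FMT or 3-month stool drop out of this analysis, so their number per arm should be reported.

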#### 1.6.3 Bloodwork

Sample collection and processing: Blood will be drawn in the morning after 12 hours fasting, based on the standard procedures at the University Health Network Laboratory Medicine Program. As insulin secretion is pulsatile, three samples will be taken at 5-min intervals, and the average of the three measurements will be calculated (165). Serum for metabolomics measurements will be collected into tubes without anticoagulant, placed on ice immediately, and centrifuged at 4°C, 2,800×g for 15 min. Serum will be aliquoted and frozen at -80°C until analysis. Samples for TNF- $\alpha$ , IL-6, and vitamin E will be collected in EDTA containing tubes, separated by centrifugation (910 × g, 10 min) and stored at -80°C until analysis. The same will be done for plasma endotoxin, but blood will be collected in pyrogen free heparin tubes (Monovette, Sarstedt, Nuernbrecht, Germany). Samples for hormone analysis will be collected in tubes containing protease inhibitors and other added chemicals described below, then separated by centrifugation (910 × g, 10 min) and stored at -80°C until analysis.

Analyses of standard blood biochemistry: The following standard tests will be performed at the Laboratory Medicine Program at the University Health Network:

Glucose: enzymatic hexokinase method (Bayer Advia 1650 Glucose package)

Insulin: microparticle enzyme immunoassay (MEIA) (Abbott Architect i2000)

Hemoglobin A1c: High-performance liquid chromatography (Variant)

C-peptide: chemiluminometric technology (Immulite 2000)

*Plasma lipids:* Triglycerides, total and high density lipoprotein (HDL) cholesterol are measured using the Abbot Architect. Low density lipoprotein (LDL) cholesterol is calculated as total cholesterol – HDL cholesterol.

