### **1.7 Statistical Considerations**

### 5.7.1 Sample size and power calculations

Our sample size is determined based on current literature, feasibility and the experience of team members, due to the pilot nature of the proposed study. Following common practice for this kind of studies (e.g. (179, 180)), we plan to recruit until we have randomized 36 eligible patients (18 per FMT

group). With a 20% attrition rate we assume that 15 patients per group will finish the intervention. This represents a greater sample size than the only previous FMT study on metabolic syndrome (26). We are confident that this sample size will allow us to investigate the stated aims.

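### The formula given for LDL cholesterol (total minus HDL) defines non-HDL cholesterol, so 'LDL' is overstated by the VLDL cholesterol if the rule is applied as written (lowest priority)

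*Combined protocol and SAP*

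**What the plan says.** Section 1.6.3 (Bloodwork) introduces the routine chemistry with "The following standard tests will be performed at the Laboratory Medicine Program at the University Health Network". For lipids it first lists what is assayed: "Triglycerides, total and high density lipoprotein (HDL) cholesterol are measured using the Abbot Architect". It then gives LDL as a derived quantity: "Low density lipoprotein (LDL) cholesterol is calculated as total cholesterol – HDL cholesterol". Blood is drawn after a 12-hour fast.

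Section 1.2 (Outcomes) places lipids under other measurements, in the run "blood lipids, gut hormones, blood pressure". Section 1.5 sets the schedule: "Baseline measurements will be repeated at 1 and 3 months post FMT". Section 5.7.2 begins the analysis with "A descriptive summary of all measurements will first be compiled", using means and standard deviations. It then names the variables for the mixed models: "The changes in the outcome variables of (HOMA-IR, weight, scores for appetite, quality of life, anxiety, and depression". LDL is not in that list.

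**The concern.** The sentence is a complete working rule, but it defines a different variable from the one it names. It has no triglyceride or VLDL term, although triglycerides are measured in the same panel. If an analyst or data manager follows it, the results table will carry a column headed LDL that holds non-HDL cholesterol.

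Two things would follow. The level would be too high at every visit and could not be compared with LDL values from elsewhere. In addition, part of any triglyceride change after FMT would appear as an LDL change, so a reader could take one lipid effect for another.

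**Working it through.** The plan gives no numerical LDL value, so there is no figure to reproduce. The check is algebra on the stated definition, followed by an illustration of size.

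**1. What the rule computes.** Total cholesterol (TC) is, apart from small remnant fractions, the sum of three parts:

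TC = HDL-C + LDL-C + VLDL-C

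Therefore TC − HDL-C = LDL-C + VLDL-C, which is non-HDL cholesterol. The excess over LDL-C is VLDL-C, which is above zero.

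**2. Is another definition given?** Section 1.6.3 lists three measured lipids: triglycerides, total cholesterol and HDL cholesterol. LDL is not among them. No other section gives an LDL assay or formula. The HOMA-IR formula that follows shortly afterwards is written out in full with its divisor, and the LDL sentence ends cleanly. Nothing suggests that a term was lost.

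**3. Size of the excess (assumed inputs).** The documents give neither a triglyceride (TG) distribution nor a divisor. Assume fasting VLDL-C = TG/k in mmol/L, with k between 3 and 2; k = 2.2 is shown as a value inside that range.

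| TG (mmol/L) | TG/3 | TG/2.2 | TG/2 |
|---|---|---|---|
| 1.0 | 0.33 | 0.45 | 0.50 |
| 1.7 | 0.57 | 0.77 | 0.85 |
| 2.0 | 0.67 | 0.91 | 1.00 |
| 3.0 | 1.00 | 1.36 | 1.50 |
| 4.0 | 1.33 | 1.82 | 2.00 |

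As an example with assumed TC 5.0 and HDL-C 1.2 mmol/L, the rule gives 5.0 − 1.2 = 3.80 whatever the triglycerides. Removing TG/2.2 gives 3.35 at TG 1.0, 2.89 at TG 2.0 and 1.98 at TG 4.0. The overstatement is then about 14%, 31% and 92% of the LDL value with VLDL removed.

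**4. Effect on change and on the comparison of arms.** Under the same assumption, a triglyceride change of Δ adds Δ/k to the 'LDL' change, that is 0.33Δ to 0.50Δ. The distortion of the between-arm contrast is the difference between arms in mean VLDL-C change. Its expected value is 0 if the arms do not differ in that respect. If triglyceride change differed between arms by 0.5 mmol/L (assumed), the carry-over would be 0.5/3 = 0.17 to 0.5/2 = 0.25 mmol/L.

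**5. Where the value would be used.** The only stated route to a report is the descriptive summary in section 5.7.2. LDL does not enter HOMA-IR, the secondary outcomes in section 1.2, the eligibility criteria, the sample size in section 5.7.1, or the results named for safety assessment in section 7.1.

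**The case against.** The strongest reply is that the sentence may never touch the data. It stands among short descriptions of routine hospital tests, and section 5.7.2 defines no LDL derivation. The laboratory may issue LDL by its own method, with this sentence as loose shorthand. That is a fair point and the documents do not settle it. It limits the certainty about a data error; it does not make the definition correct. Even on that reading, the protocol misdescribes how the variable was obtained.

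A second reply is that the consequence is minor. LDL is not named as an endpoint, and its reporting is only implied by the general promise to summarise all measurements. This also stands, and it is why the point ranks last.

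A third reply concerns size: the triglyceride levels and divisors come from outside the documents. They do, so the figures are illustrations and the algebra carries the point. Nor is there evidence in the documents that triglyceride change will differ by arm. With "15 patients per group will finish the intervention" expected, chance differences can arise, but that is true of every measurement in a trial this small and is not caused by this sentence.

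**Conclusion.** The concern holds. As written, section 1.6.3 defines non-HDL cholesterol and calls it LDL cholesterol. That conclusion rests only on the composition of total cholesterol. It is firm for the wording and conditional for the data: values are wrong only if the rule is actually applied.

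If it is applied, the excess equals the VLDL cholesterol. It is roughly 0.6 to 0.9 mmol/L at triglycerides of 1.7 mmol/L, and 0.33 to 2.00 mmol/L over triglycerides of 1.0 to 4.0 mmol/L, assuming VLDL cholesterol between TG/3 and TG/2. The between-arm contrast is not biased in expectation unless VLDL cholesterol change differs by arm. No main or secondary outcome, eligibility rule or sample-size figure uses LDL. This is a correction worth making, at the lowest priority.

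**What to change.** Ask the laboratory how it obtains LDL cholesterol, and replace the sentence in section 1.6.3 with that formula (including its triglyceride term and any triglyceride limit on its use) or with the name of the direct assay. If total minus HDL is what will be computed, call it non-HDL cholesterol in the protocol, the dataset and the tables.

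The cost is one sentence. All three components come from the fasting blood sample already planned, so values can be relabelled or recalculated before reporting, with no new samples and no loss of data.
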